#### **9.2.4 Assessment of MCM and ALM Gene Expression Profiling**

Analysis will utilize matched paired of (i) tumor, and (ii) normal adjacent stromal tissue from pre-treatment and (optional) on-treatment samples. Tissue dissection will be done by means of macrodissection. Paired normal tissue will serve as internal control for each patient's tumor and tumor and normal stromal tissue will undergo RNA extraction according to standard FFPE DNA&RNA extraction protocol. This process will be performed simultaneously with DNA extraction using the same starting FFPE or frozen tissue material. Poly(A) enrichment, RNA fragmentation, library preparation, automated cluster generation, paired-end sequencing, base calling and mapping will be performed. Following RNA-sequencing, raw data will undergo standard bioinformatic analysis. BAM files will be converted to merged, demultiplexed FASTQs. Paired-end reads will be mapped to the UCSC hg19 human transcriptome using specific algorithm to allow alignment of sequence with single base changes due to point mutations. Expression level of genes will be quantified using Li et. al algorithm or equivalent method ( $E_{i,j} = \log_2(TPM_{i,j}/10+1)$ , where  $TPM_{i,j}$  refers to transcript-per-million (TPM) for gene  $i$  in sample  $j$ , as calculated by RSEM(64) v1.2.3 in paired-end mode) Gene expression profiling analysis will be performed at MD Anderson Cancer Center under a direction of Drs. [name] and [name] at the end of the study.

#### **9.2.5 Analysis of putative tumor neoantigen epitopes**

Sequence annotation and variant data from each patient at pre-treatment baseline will be used for computational analysis to validate neoantigen peptides-MHC class I binding prediction algorithm. The prediction will generate a set of candidate T-cell epitopes that could bind to patient's MHC class I alleles, and determine binding affinity between patient's specific neoantigen epitopes and patient's MHC class I alleles *in silico*.

The analysis will be performed by [name] at department of Biostatistics & Bioinformatics, Georgetown University-Lombardi Comprehensive Cancer Center.

#### **Human Leukocyte Antigen Testing**

High-resolution Human leukocyte antigen (HLA) typing information from each participant will be extracted from whole exome sequencing data obtained from whole blood (genomic DNA). The analysis will be performed at University of Colorado ([name]) at the end of the study.

Please refer to Laboratory Manual for detailed instruction on specimen collection, processing, storage and shipment.

#### **9.2.6 Assessment of Tumor Immune Cells Infiltrates and PD1+ Cells at Invasive Margin**

Planned analyses include immunohistochemistry (IHC) for PD-1, PD-L1+, CD28, CD3, CD4, CD8, CD45RO, FoxP3, Granzyme B, CD14, CD20, DAPI, Pan Melanoma Cocktail (HMB45, MART-1, Tyrosinase), and Ki-67+ expression, and quantification of immune cells infiltrates, and co-inhibitory/co-stimulatory marker-positive cells at the invasive tumor margin by multiplex immunohistochemistry and digital pathology system. The study will be performed at G-LCCC under a direction of Drs. [name] and [name]. Additional IHC markers may be added based on available information from MRFBC Consensus information.

Please refer to Laboratory Manual for detailed instruction on specimen collection, processing, storage and shipment.

#### 9.2.7 Assessment and Monitoring of T-Cell Receptor Rearrangement

Planned analyses include assessment of TILs T-cell receptor β-chain genes using ImmunoSeq® platform. The analyses will assess the baseline TCR recombination (unique TCR sequences, clonal frequency distribution, and TCR diversity) between variable (V), joining (J), and diversity (D) segments that result in unique sequences in the antigen-binding site, as well as the effect of combined immune checkpoint inhibitor therapy on V(D)J rearrangement of TCR. Specimens for TCR rearrangement assay will be batched and sent from G-LCCC to Adaptive Biotechnology for analyses at the end of the study. Data analysis will be performed by [name] at G-LCCC.

Please refer to Laboratory Manual for detailed instruction on specimen collection, processing, storage and shipment.

### 9.3 Studies to be performed on blood

Peripheral blood samples will be collected on all patients prior to initiation of checkpoint inhibitors therapy and during treatment.

Serum will be used in circulating nucleic acids analyses. One additional 10ml tube of blood at each specimen collection step has been incorporated into the protocol to exclusively store as a part of MRFBC Virtual Repository and for future research.

At the conclusion of the therapy for each patient, specimens should be batched and transported to G-LCCC-Histopathology Shared Resource (HTSR) c/o [name] at the provided address for assessment of circulating cell-free nucleic acids. Circulating nucleic acid analyses will be done under the direction of [name] at GU-LCCC.

Please refer to Laboratory Manual for detailed instruction on specimen collection, processing, storage and shipment.

### 9.3.1 Assessment of Pretreatment and Serial Levels of Circulating Cell-Free Nucleic Acids

All patients will have plasma and serum collected at pre-treatment, every 6 weeks on-treatment, and at PD. Guidelines for isolation of plasma and serum are outlined in Section 9.3. Each sample will be linked to the corresponding tumor and labeled with non-identifiable coding system designated for each tumor.

Information on mutant DNA enriched in each tumor will be extracted from WES analyses. The analysis will assess circulating cell-free mutant DNA from the top most enriched mutations in each patient's tumor, in addition to a panel of cancer related genes. Circulating cell-free mutant DNA analysis will be performed on Illumina HiSeq system with TruSeq Nano Sample Preparation Kit (or equivalent system) to detect and quantify the circulating mutation load per ml of serum. The frequency of circulating mutant DNA will be assessed at baseline, at 6 weeks interval, and at RECIST-defined disease progression. The kinetics of circulating cell-free mutant DNA compared to baseline will be compared with radiographic response (per RECIST v.1.1) to establish the relationship between circulating mutant DNA burden and response to combined immune-checkpoint blockade.

Serum samples from each patient may be used to analyze for circulating non-coding RNA (i.e. miRNA) and exosomal substrates (i.e. protein, miRNA, snRNA)

We will attempt to establish predictive circulatory biomarker that could separate responders from non-responders in MCM and ALM cohorts

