### 9.3.2 Sample Submission Schedule

- Blood samples will be taken  $\leq$  7 days prior to treatment of checkpoint inhibitors.
- **Two** 10ml Cell-Free DNA BCT® tubes (StreckTM; Omaha, NE), **two** 10ml CPTTM Mononuclear cell preparation tube and **one** 10ml serum separators (red-top

SST) will be drawn at pre-treatment.

- **Two** 10ml Cell-Free DNA BCT® tube (Streck™; Omaha, NE) One 10ml CPT™ Mononuclear cell preparation tube and **One** 10ml serum separators (red-top SST) will be drawn every 6 weeks during treatment and at the time of disease progression.

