## Appendix G

### Specimen Submission Guidelines

Baseline tumor: tumor block or 26 unstained FFPE slides from primary or met; preferred excisional or punch (if not possible 14-16 gauge core needle)						
Correlative Study	Sample required at each time point	Baseline	6-8 wks  after tx	Every 6 wks during tx	Disease Progression	Shipping/ Storage for Future Use
Baseline correlative Studies on Tissues	Tumor block or 16 unstained FFPE tumor tissue slides at 10-micron	XX				Ship to GU-LCCC-HTSR ([name]) at the end of the study. Leftover specimens (if any) stored at GU-LCCC-HTSR & placed in MRFBC VR for future use
	Tumor Block or 10 unstained FFPE tumor tissue slides at 5-micron	XX				
(Optional) On-treatment correlative Studies on Tissues	1. Frozen tumor embedded in OCT at-80c 2. FFPE tumor block		XX			Ship to GU-LCCC-HTSR ([name]) at the end of the study. Leftover specimens (if any) stored at GU-LCCC-HTSR & placed in MRFBC VR for future use

1 Expect 25% of patients (N=15; 10 MCM and 5 ALM patients) to consent to on-treatment biopsies

2 Blood samples will be taken  $\leq$  7 days prior to treatment

3 Specimens should be batched shipped to GU-LCCC-GESR at the conclusion of therapy for each patient. (at the end of the trial)

Correlative Study	Sample required at each time point	Baseline	3 wks  after tx	Every 6 wks during tx 	Disease Progression or at the end of study	Shipping/ Storage for Future Use 
High-resolution HLA typing	CPT TM Mononuclear cell preparation tube blood	XX; 10ml				Ship to GU-LCCC-HTSR ([name]) at the end of the study.
Blood Correlates	Blood in Cell-Free DNA BCT ® tubes (Streck TM ) -Red-top blood -CPT TM Mononuclear cell preparation tube blood	XX  20ml blood in Cell-Free DNA BCT ® tubes; 10ml red-top blood, 10ml CPT TM tube blood (collect within 7 days prior to treatment)		XX  20ml blood in Cell-Free DNA BCT ® tube; 10ml red-top blood; 10ml CPT TM tube blood	XX  20ml blood in Cell-Free DNA BCT ® tube; 10ml red-top blood; 10ml CPT TM tube blood	Ship to GU-LCCC-HTSR ([name]) at the end of the study.; Leftover specimens (if any) stored at GU-LCCC-GESR & placed in MRFBC VR for future use

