Microbiota Correlates	Stool in Omnigene.Gut collection tube	XX (collect ≤ 7 days prior to Rx up to within 24 hours of receiving first dose)	XX (collect ≤ 5 days prior to Rx)		XX (+/- 7 days)	Ship to GU-LCCC-HTSR ([name]) at the end of the study.

All samples should be shipped overnight to:

GU-LCCC Histopathology Shared Resource (HTSR)-MRFBC Mucosal & Acral Melanoma Tissue Bank

c/o [name]

Georgetown-Lombardi Comprehensive Cancer Center  
[name]

 Expect 25% of patients (N=15; 10 MCM and 5 ALM patients) to consent to on-treatment biopsies

[figure not shown]
 Blood samples will be taken ≤ 7 days prior to treatment

 Specimens should be batched shipped to GU-LCCC-GESR at the conclusion of therapy for each patient. (at the end of the trial)

 Red-top tubes will be subsequently processed into serum, which will be aliquotted into 1ml aliquots & stored at -80C.

Cell-free DNA BCT® tube (StreckTM) will be subsequently processed into plasma (which will be aliquotted into 1ml aliquots & stored at -80C) and PBMC. Please refer to the protocol guideline in blood component preparation

[name]  
[name]

Materials are to be shipped SUNDAY THROUGH THURSDAY only. Do not ship samples the day before a Holiday

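### The circulating mutant DNA assay is specified on serum, while the Cell-Free DNA tubes drawn at every blood time point become plasma for which the protocol names no assay

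*Combined protocol and SAP*

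**What the plan says.** Serum is specified twice, once as the matrix and once as the unit. Section 9.3 states: "Serum will be used in circulating nucleic acids analyses". Section 9.3.1 describes a sequencing assay to "detect and quantify the circulating mutation load per ml of serum", whose change from baseline is then compared with RECIST response.

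Collection is broader than that. Section 9.3.1 opens with "All patients will have plasma and serum collected at pre-treatment, every 6 weeks on-treatment, and at PD". The pre-treatment list in Section 9.3.2 includes "Two 10ml Cell-Free DNA BCT" tubes and "one 10ml serum separators (red-top SST"). The same numbers of these two tube types "will be drawn every 6 weeks during treatment and at the time of disease progression". Appendix G agrees, giving "20ml blood in Cell-Free DNA BCT" tubes and 10 ml of red-top blood at each of these points. Its footnotes 7-9 say that the red-top tubes become serum and that the Cell-Free DNA tube "will be subsequently processed into plasma", stored frozen in 1 ml aliquots, and PBMC.

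Three further provisions matter:
- Section 9.3.1 allows the serum to be used for non-coding RNA and exosome work as well.
- Section 9.3 reserves one additional 10 ml tube per collection for the repository, without naming its type.
- Section 9.3.3 has the study supply the Cell-Free DNA tubes, while sites provide their own serum tubes.

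**The concern.** The protocol supplies a tube made for cell-free DNA, draws two of them at every blood time point, and stores the plasma. It then specifies its only described cell-free DNA assay on the other tube. Followed literally, the assay draws on the smaller collection, which it may have to share with RNA and exosome work, while the purpose-collected plasma has no stated use.

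Exploratory objective 2.10 is at stake. It looks for circulating nucleic acid patterns associated with response or resistance, and Section 9.3.1 serves it through serial change in mutant DNA. There is also a plain ambiguity. A laboratory that uses the plasma departs from the written unit. One that uses the serum leaves 20 ml of blood per draw without a stated analysis. Matrix and unit should be fixed before any sample is assayed.

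**Working it through.** **1. Volumes drawn.** From Section 9.3.2:
- Cell-Free DNA tubes: 2 x 10 = 20 ml.
- Serum tube: 1 x 10 = 10 ml.
- Ratio of blood drawn: 20 / 10 = 2.0, at pre-treatment, every 6 weeks and at progression.

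Check against Appendix G, using all tubes:
- Pre-treatment, Section 9.3.2: 20 + 20 (two CPT tubes) + 10 = 50 ml. Appendix G: 20 + 10 + 10 + 10 (CPT tube for HLA typing) = 50 ml.
- Later draws: 20 + 10 + 10 = 40 ml in both places.

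The two schedules agree, so the 2:1 draw is not a slip in one table.

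**2. Volume available to the assay.** The documents give no plasma or serum yield, so equal yield per ml of blood is assumed.
- If the repository tube is not one of the two Cell-Free DNA tubes: 20 / 10 = 2.0.
- If it is one of them: (20 - 10) / 10 = 1.0.

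The range is therefore 1.0 to 2.0. Any serum taken for miRNA or exosome work would reduce the serum side; the documents do not say by how much.

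**3. What each specimen is assigned to.**

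| Specimen | Source | Named use in the protocol text |
|---|---|---|
| Serum | one 10 ml tube | circulating nucleic acids; mutant DNA per ml; possibly miRNA and exosomes |
| Plasma | two 10 ml Cell-Free DNA tubes | collected and stored; no assay named |

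The study overview in Section 5.1 mentions separating PBMCs and serum and omits plasma.

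**4. Illustration of what volume could do.** Assumptions, none from the documents: half of the blood volume is recovered, the whole sample is used, DNA recovery is complete, and fragments follow a Poisson distribution. The probability of at least one mutant fragment is 1 - exp(-c x V), with c fragments per ml and V ml assayed. Plasma is V = 20 x 0.5 = 10 ml at ratio 2.0, or 5 ml at ratio 1.0. Serum is V = 10 x 0.5 = 5 ml.

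| c per ml | Plasma, ratio 2.0 | Plasma, ratio 1.0 | Serum |
|---|---|---|---|
| 0.1 | 1 - exp(-1) = 63% | 39% | 1 - exp(-0.5) = 39% |
| 0.2 | 1 - exp(-2) = 86% | 63% | 1 - exp(-1) = 63% |
| 0.3 | 1 - exp(-3) = 95% | 78% | 1 - exp(-1.5) = 78% |
| 1.0 | 1 - exp(-10) > 99.9% | 99.3% | 1 - exp(-5) = 99.3% |

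Section 9.3.1 tracks several mutations. With five independent ones assumed at 0.1 per ml each, detecting at least one has probability 1 - exp(-0.5 x 10) = 99% in 10 ml against 1 - exp(-0.5 x 5) = 92% in 5 ml.

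**The case against.** The strongest reply is that this is loose wording rather than a decision to leave the plasma unused. Section 9.3.1 itself opens by collecting both plasma and serum, and Section 9.3 ships specimens in general, not serum alone, for the cell-free assessment. The separate Laboratory Manual (Appendix H) and the text between Sections 9.3.3 and 9.3.5 were not available and might assign the plasma. This stands as a limit: a reader might infer that the plasma has no assay at all, but the documents support only that none is named in the available text. It does not remove the mismatch, because serum is written as both matrix and unit.

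The repository tube is also a fair objection. On treatment, the Cell-Free DNA tube is the only type drawn in duplicate, so it is a plausible candidate. If so, the volume advantage disappears. This stands, and it is why the ratio is given as a range.

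A reader might infer a real loss of detection from 63% to 39%. The documents do not support that. The concentrations and recovery are assumed, the low values chosen are where volume matters most, and tracking several mutations narrows the gap. A reader might also argue that clotting releases normal blood-cell DNA and dilutes the mutant fraction. The documents say nothing on this, and a load per ml is not itself changed by added wild-type DNA, so the point does not rest on it.

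Finally, one matrix at all time points lets change from baseline compare like with like within a patient. That is correct for serum, and equally for plasma.

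**Conclusion.** The point holds as a mismatch between the specimen collected for cell-free DNA and the specimen the assay is written for. The firm figure is the 2:1 ratio of blood drawn. The usable ratio is 1.0 to 2.0, given equal yields per ml of blood and depending on the repository tube. The detection figures only illustrate the direction and are nil at ratio 1.0.

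The consequence is confined to exploratory objective 2.10. A reader should not infer any effect on the primary response-rate analysis, the sample size, PFS or OS, since none of these uses the blood assay. This is an inexpensive improvement, not a flaw in the trial's main conclusions.

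**What to change.** - In Sections 9.3 and 9.3.1, name plasma from the Cell-Free DNA tubes as the matrix for circulating mutant DNA at every time point, and give the unit as per ml of plasma.
- Keep serum for the miRNA and exosome work already listed.
- State which tube type is the repository tube, so that the volume left for the assay is known.
- Align Section 5.1, Appendix G and the Laboratory Manual with that choice.

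The cost is wording. The plasma is already drawn, divided into aliquots and frozen, so no tube, visit or procedure is added. The change should be made before any sample is assayed. If the laboratory has a reason to prefer serum, the protocol should say so and state what the plasma is for.

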### 9.3.2 Sample Submission Schedule

- Blood samples will be taken  $\leq$  7 days prior to treatment of checkpoint inhibitors.
- **Two** 10ml Cell-Free DNA BCT® tubes (StreckTM; Omaha, NE), **two** 10ml CPTTM Mononuclear cell preparation tube and **one** 10ml serum separators (red-top

SST) will be drawn at pre-treatment.

- **Two** 10ml Cell-Free DNA BCT® tube (Streck™; Omaha, NE) One 10ml CPT™ Mononuclear cell preparation tube and **One** 10ml serum separators (red-top SST) will be drawn every 6 weeks during treatment and at the time of disease progression.

#### 9.3.3 Sample Preparation Guidelines

A batch of Cell-Free DNA BCT® tubes will be distributed to each participating site as the patients are being registered to the study. Each site will provide their own CPT™ Mononuclear cell preparation tube and serum separators (red-top SST) tubes. All samples will be processed locally at each participating institution according to the laboratory manual (see Section 9.3). PBMCs, serum and plasma will be stored at -80°C freezer at each participating institution. Specimen will be batched and shipped on dry ice overnight to G-LCCC HTSR (attn. [name]) at the end of the study. Specimen will be stored under MRFBC Mucosal & Acral Melanoma Tissue Bank.

#### 9.3.5 Collection

All blood samples will be stored in the MRFBC Virtual Specimen Repository and then batch shipped to G-LCCC.

#### 9.4 Study to be performed on Stool

In this study, collection of stool will occur at baseline (within 7 days prior to starting treatment up to within 24 hours of the first treatment), at 3 weeks into the treatment (+/- 5 days), and at the time of disease progression or study conclusion (+/- 7 days), as indicated on Appendix E.

At the conclusion of the therapy for each patient, specimens should be batched and transported to GU-LCCC-Tissue Culture Shared Resource (TCSR) c/o [name] at the provided address in Appendix B. Gut microbiota analyses will be done under the direction of Drs. [name] and [name] at MD Anderson Cancer Center.

Please refer to Laboratory Manual for detailed instruction on specimen collection, processing, storage and shipment.

##### 9.4.1 Effects of Gut Microbiota and Anti-Tumor Activities and Effects of Combined Immune Checkpoint Inhibitor Therapy on Gut Microbiota in MCM and ALM

At the end of the study, genomic DNA will be isolated from fecal samples using QIAamp DNA Stool Mini Kit (Qiagen), or equivalent brand, following the manufacturer's instruction. Targeted qPCR system will be applied using either Taqman technology (for systems targeting all bacteria domain and Bacteroidetes/Prevotella group) or SYBRGreen (for different Bacteroides species) Quantitative -PCR will be performed using ABI PRISM 7300 qPCR system or equivalent.

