#### **1.8.7 Gut Microbiota and Immune Checkpoint Inhibitor Therapy**

Recent breakthrough studies have demonstrated that, in mouse models, certain intestinal microbiomes, i.e. *Bacteroides fragilis* and *Bifidobacterium* sp. altered the response of cutaneous melanoma in mouse model to the anti-PD-1 and anti-CTLA-4 monoclonal antibodies. Further studies into *Bifidobacterium* demonstrated that the bacteria alters dendritic cell activity, which led to improvement of tumor-specific CD8+ T cell activity, and delays in melanoma growth (58, 59). It is not clear whether intestinal microbiomes in variant melanoma have similar or distinct immunomodulatory effects against tumor and affect the activity of immune checkpoint blockades.

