#### Exploratory Objective

2.6 To evaluate tumor's putative neoantigen epitopes from le exome sequencing data and determine binding affinity to MHC class I molecules as a potential predictor of response to combined checkpoint inhibitors treatment

2.7 To determine clonal preservation, expansion, and selection of T-cell receptor rearrangement of tumor infiltrating lymphocytes before and after treatment with combined ipilimumab/nivolumab therapy as a correlative biomarker of treatment response

2.8 To identify MCM and ALM gene expression profiling pattern associated with treatment response or resistance to combined checkpoint inhibitors treatment

2.9 To identify relationship of specific gut microbiota in MCM and ALM with CD8+T cell function and anti-tumor immunity

2.10 To identify circulating cell-free nucleic acids and its pattern that might be associated with combined checkpoint inhibitor treatment response/resistance in order to further narrow the application of combined checkpoint inhibitors to those who will benefit the most

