## 10.3 Statistical Analysis for Correlative Studies

### 10.3.1 Best Overall Response

The proportion of patients achieving a response (best overall response; complete or partial response as per RECIST v1.1 criteria (outlined in appendix C) and exact binomial 95% CI will be calculated. Objective response rates (complete response + partial response) will be calculated separately for each cohort.

Among all enrolled patients, additional hypothesis-generating analyses will be undertaken to explore whether somatic mutational loads, difference in driver mutation profiles, level of pre-treatment CD8+ TIL and PD-L1 expressing cells at the invasive tumor margin, presence of tumor specific neoantigen, TCR clonality, gene expression profiles and enrichment of specific gut microbiota might be associated with responsiveness in order to further refine the optimal population for treatment with ipilimumab and nivolumab combination in MCM and ALM.

Categorical factors and continuous factors will be compared between responders and non-responders using Fisher's exact tests and two-sample Wilcoxon rank sum test respectively.

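### The stool qPCR panel in section 9.4.1 has no Bifidobacterium target, so that organism cannot be quantified separately from total bacteria

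*Combined protocol and SAP*

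**What the plan says.** Section 1.8.7 gives the scientific background for the stool work. It reports that in mouse models certain intestinal organisms, "i.e. *Bacteroides fragilis* and *Bifidobacterium* sp. altered the response of cutaneous melanoma" to checkpoint antibodies. It then turns to Bifidobacterium alone and says that further studies "demonstrated that the bacteria alters dendritic cell activity, which led to improvement of tumor-specific CD8+ T cell activity". It closes by leaving open whether the microbiome acts in the same way in variant melanoma.

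Objective 2.9, one of the exploratory objectives, is "To identify relationship of specific gut microbiota in MCM and ALM with CD8+T cell function and anti-tumor immunity". It names no organism.

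Section 9.4.1 describes the laboratory method as targeted qPCR by one of two chemistries, TaqMan or SYBR Green, and its target list reads "systems targeting all bacteria domain and Bacteroidetes/Prevotella group) or SYBRGreen (for different Bacteroides species". A particular instrument is named, with a comparable one allowed. DNA extraction from stool is placed at the end of the study.

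Section 10.3.1 uses the data in a hypothesis-generating analysis of whether "enrichment of specific gut microbiota might be associated with responsiveness". Categorical factors are compared between responders and non-responders by Fisher's exact test, and continuous factors by the Wilcoxon rank sum test.

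**The concern.** A targeted qPCR assay reports only what its primers and probes cover. If an organism that motivates the work has no primer set of its own, its abundance never becomes a variable in the dataset, and the comparison in section 10.3.1 cannot be made for it.

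Bifidobacterium appears to be in that position. It is also the only organism to which the protocol attributes the CD8+ T-cell effect that objective 2.9 echoes. At stake is the interpretation of an exploratory result. A reader of the final report who knows section 1.8.7 could take silence on Bifidobacterium, or a null microbiota finding, as evidence about that organism when it was never assayed.

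**Working it through.** No power or error-rate calculation applies, and the plan states no figure to reproduce. The check sets the organisms in the background against the targets in the assay section.

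**Step 1. Organisms cited (section 1.8.7).** Two: Bacteroides fragilis and Bifidobacterium. The CD8+ T-cell mechanism is attributed to Bifidobacterium.

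**Step 2. Targets listed (section 9.4.1).** Three sets:
- all bacteria, at domain level (TaqMan);
- the Bacteroidetes/Prevotella group (TaqMan);
- different Bacteroides species (SYBR Green).

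**Step 3. Match.**

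| Organism in 1.8.7 | Target in 9.4.1 that can report it separately |
|---|---|
| Bacteroides fragilis | Can be accommodated in the Bacteroides species set; its wider group is covered by Bacteroidetes/Prevotella |
| Bifidobacterium | None; it contributes only to the all-bacteria total |

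The second row relies on Bifidobacterium lying outside the Bacteroidetes. That is general taxonomy and is not stated in the protocol.

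**Step 4. Can the organism be recovered by subtraction?** No. All bacteria minus the Bacteroidetes/Prevotella group leaves every other bacterium together, with Bifidobacterium as an unknown part of it.

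**Step 5. Is there flexibility elsewhere?** The or-equivalent wording in section 9.4.1 attaches to the brand of extraction kit and to the qPCR instrument, not to the targets. No 16S, shotgun or other untargeted sequencing of stool is described anywhere in the supplied text.

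**Step 6. Number of samples.** Section 10.2 plans 49 patients with mucosal melanoma and 24 with acral lentiginous melanoma: 49 + 24 = 73. Sections 9.4 and 9.4.2 give three stool time points: baseline, three weeks, and progression or end of study. The maximum is 73 × 3 = 219 samples. This is a ceiling. Eligibility criterion 3.1.4 requires willingness to give blood and does not mention stool, and the third sample depends on reaching progression or the end of the study.

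**The case against.** Several points on the other side stand.

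**The objective names no organism.** Objective 2.9, section 10.1 and section 10.3.1 all speak of specific microbiota in general. The two organisms appear only in the background, as mouse findings. A reader might infer that the trial's microbiota objective is a test of Bifidobacterium and therefore cannot be answered. The documents do not support that. The link is an inference from section 1.8.7, though a reasonable one, because the CD8+ wording of the objective matches the effect described there for Bifidobacterium.

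**The panel is not empty.** A reader might also infer that a null microbiota result would be uninformative. That goes too far. The panel covers total bacteria, the Bacteroidetes/Prevotella group and Bacteroides species, and a null result would inform on those.

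**Nothing is lost at collection.** Stool is stored frozen, and DNA is extracted only at the end of the study. The samples still hold the information; the gap is in what the plan says will be measured.

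**The Laboratory Manual might list more targets.** It is a separate document (Appendix H) and was not available, so a fuller primer list cannot be excluded. This argument is weak. Section 9.4 cites the manual for handling only ("Please refer to Laboratory Manual for detailed instruction on specimen collection, processing, storage and shipment"), while section 9.4.1 specifies the targets itself. If the manual does hold a wider panel, section 9.4.1 needs only a short correction.

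**The aim is exploratory.** This is true, and it sets the weight of the point. It does not remove the mismatch between background and assay.

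**Conclusion.** The point holds in a limited form. As written, section 9.4.1 leaves one of the two organisms cited in section 1.8.7 without a target, and it is the one given the CD8+ T-cell mechanism. Whatever the panel shows, it will inform on Bacteroides-group taxa and on total bacterial load, and will say nothing specific about Bifidobacterium.

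The consequence is confined to one exploratory objective and a hypothesis-generating comparison. The primary response-rate analysis and the sample size do not change. This is a worthwhile improvement, not a defect that threatens the trial.

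The conclusion rests on three assumptions: the target list in section 9.4.1 is complete, the Laboratory Manual does not extend it, and Bifidobacterium is not amplified by the Bacteroidetes/Prevotella or Bacteroides systems.

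**What to change.** Add a Bifidobacterium-specific primer set to the panel in section 9.4.1, run on the same extracted DNA at the end of the study. In section 10.3.1, include Bifidobacterium abundance among the taxa compared between responders and non-responders; as a continuous factor it falls under the Wilcoxon rank sum test already planned. Do not restrict that comparison to two taxa, since that would be narrower than objective 2.9.

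If the target is not added, state in objective 2.9 that conclusions are limited to the taxa assayed. An untargeted sequencing method would also close the gap, but it is a larger change.

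The cost of the preferred change is one further qPCR target on at most 219 samples: a small reagent cost, with no new samples, visits or burden on patients. Because the assays come at the end of the study, the change can be made before any of them is run. The wording alternative costs one sentence.
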